### **Adverse Events**

All adverse events occurring on or after the shorter infusion (including the safety follow-up period) will be coded, summarized by NCI CTCAE v4.0 grade, and tabulated by body system and Preferred Term for individual adverse events within each body system. All adverse events, Grade 3 to 5 adverse events, serious adverse events, adverse events leading to treatment discontinuation, time to withdrawal from the study due to an adverse event, adverse events leading to infusion adjustment, and treatment-related adverse events will be summarized. In addition, all serious adverse events and deaths will be listed if applicable.

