5.3.5.4 Persistent or Recurrent Adverse Events

A persistent adverse event is one that extends continuously, without resolution, between patient evaluation timepoints. Such events should only be recorded once on the Adverse Event eCRF. The initial severity (intensity or grade) of the event will be recorded at the time the event is first reported. If a persistent adverse event becomes more severe, the most extreme severity should also be recorded on the Adverse Event eCRF. If the event becomes serious, it should be reported to the Sponsor immediately (i.e., no more than 24 hours after learning that the event became serious; see Section 5.4.2 for reporting instructions). The Adverse Event eCRF should be updated by changing the event from "non-serious" to "serious," providing the date that the event became serious, and completing all data fields related to serious adverse events.

A recurrent adverse event is one that resolves between patient evaluation timepoints and subsequently recurs. Each recurrence of an adverse event should be recorded as a separate event on the Adverse Event eCRF.

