Appendix 2 **Optional Shorter Infusion Substudy (cont.)**

Vital signs should be taken approximately 45 minutes prior to premedication. In addition, vital signs should be obtained prior to the ocrelizumab infusion and then approximately every 15 minutes for the first hour, followed by approximately every 30 minutes until 1 hour after the end of the infusion.

Patients will be informed about the possibility of delayed post-infusion symptoms and instructed to contact their study physician if they develop such symptoms.

SUBSTUDY FOLLOW-UP

Patients should have substudy follow-up 30 days after the date of the last infusion of ocrelizumab in this substudy, consisting of one clinic visit. After 30 days, patients may continue to be followed per the main study safety follow-up if they do not continue onto commercial ocrelizumab.

STATISTICAL METHODS

Safety Analyses

Safety analyses will include all patients who received any amount of study treatment in the substudy.

Safety will be summarized using descriptive statistics. Continuous variables will be summarized using n (sample size), mean, standard deviation, median, minimum, and maximum. Frequency distributions (patient counts and associated percentages) will be used to summarize categorical variables. When applicable, 95% confidence intervals (CIs) will be provided for the mean and proportion. The Clopper and Pearson method will be used to calculate exact CIs for proportion when applicable.

All adverse events occurring on or after treatment will be coded, summarized by NCI CTCAE v4.0 grade, and tabulated by body system and Preferred Term for individual adverse events within each body system. Grade 3 to 5 adverse events, serious adverse events, adverse events leading to treatment discontinuation, time to withdrawal from the study due to an adverse event, adverse events leading to infusion adjustment, and treatment-related adverse events will be summarized. In addition, all serious adverse events and deaths will be listed.

Associated laboratory parameters, such as hepatic function, renal function, and hematology values, will be grouped and presented together. Marked abnormalities will also be flagged.

Ocrelizumab exposure will be summarized, including rate of infusion and dosage.

Ocrelizumab—Genentech, Inc.
84/ Protocol MN30035, Version 5

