## **4. STATISTICAL METHODS**

For continuous variables, descriptive statistics (e.g., mean, median, standard deviation [SD], n, 25th and 75th percentiles, minimum, maximum) will be calculated and summarized. For categorical variables, the number and percentage in each category will be displayed. Statistical methods for analysis of efficacy variables are detailed in the Efficacy Analyses section below.

Planned analyses for the shorter infusion sub-study will be described in Appendix 6.

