## 4.7 SAFETY ANALYSES

All safety analyses will be based on the safety population. For all change from baseline analyses, unless noted otherwise, baseline will be defined as the last non-missing value on or before the first infusion.

Treatment emergent AEs (TEAEs) are defined as AEs that occur on or after treatment on Day 1 or existing events that worsened after first study dose. Treatment emergent serious AEs (SAEs) are defined as SAEs that occur on or after treatment on day 1 or existing events that increased in severity after first study dose. AEs will be coded using the current MedDRA Dictionary and summarized by NCI CTCAE v4.0 grade.

Relapse is part of the efficacy outcome as a component of protocol defined events and will be reported in the efficacy results section.

Visit windows will be used in analyses that summarize laboratory measurements, vital signs. Visit window specifications will be provided in the separate Module 2.

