### **Outcome Measures**

The primary objective of the substudy is to evaluate the rate and severity of IRRs of the ocrelizumab 600-mg infusion administered over the course of approximately 2 hours, instead of the currently approved duration of 3.5 hours, in patients with MS who have had prior treatment with ocrelizumab in study MN30035 (CHORDS), as measured by the rate and frequency of National Cancer Institute Common Terminology Criteria for Adverse Events, Version 4.0 (NCI CTCAE v4.0) Grade 3 and 4 IRRs. Specifically, the safety outcome measures are listed below.

- Rate and frequency of Grade 3 or 4 IRRs with onset on or after the shorter ocrelizumab infusion at Week 96 and at the substudy follow-up
- Changes in physical findings and vital signs with onset on or after the shorter ocrelizumab infusion at Week 96 and at the substudy follow-up

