### **Summary of IRRs**

The number and proportion of patients in the substudy who experienced Grade 3 or 4 IRRs with onset on or after the shorter infusion (including the safety follow-up period) will be summarized with the associated 95% exact confidence interval. The 2-sided 95% exact confidence interval will be calculated using the Clopper and Pearson method.

The incidence rate and the 2-sided 95% exact confidence interval will also be calculated for all Grade 1-4 IRRs.

The number and proportion of patients in the substudy who experienced local IRR and systemic IRR will also be summarized with 95% exact confidence interval.

Listings of Grade 3 or 4 IRRs, and IRRs that led to interruption of the shorter infusion or treatment withdrawal will be provided, if applicable, on the symptom of the IRR, CTCAE grade, infusion rate at the onset of IRR, action taken on ocrelizumab administration following the IRR, and the history of IRR events during the long infusion study period (e.g., highest CTCAE grade, frequency)

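### The shorter infusion substudy's adverse event tables have no rule for an ongoing event that worsens after the infusion, although the main-study definition has one

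*SAP*

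**What the plan says.** **Main study.** SAP 4.7 (Safety Analyses) defines treatment-emergent AEs as "AEs that occur on or after treatment on Day 1 or existing events that worsened after first study dose". Serious events are handled the same way: "SAEs that occur on or after treatment on day 1 or existing events that increased in severity after first study dose". Both definitions have two limbs, and both take the first study dose as reference.

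**Substudy.** SAP Appendix 6 (Adverse Events) begins "All adverse events occurring on or after the shorter infusion (including the safety follow-up period) will be coded" and then lists the tables: all AEs, Grade 3 to 5, serious, leading to discontinuation, leading to infusion adjustment, and treatment-related. Protocol Appendix 2 (Safety Analyses) says "All adverse events occurring on or after treatment will be coded, summarized by NCI CTCAE v4.0 grade". Neither mentions worsening of an event already present. For examination findings, Appendix 6 (Outcome Measures) goes by onset: "Changes in physical findings and vital signs with onset on or after the shorter ocrelizumab infusion at Week 96".

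**Which section governs.** SAP section 4 states: "Planned analyses for the shorter infusion sub-study will be described in Appendix 6".

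**Recording.** Under Protocol 5.3.5.4 a persistent AE has one record, which holds its initial severity. The protocol adds: "If a persistent adverse event becomes more severe, the most extreme severity should also be recorded on the Adverse Event eCRF". The date of any change to serious is entered as well. No date is named for a rise in grade.

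**The concern.** The substudy is meant to evaluate the safety and tolerability of a 600 mg infusion given over about 2 hours instead of 3.5. Its patients arrive with about 96 weeks of AE recording behind them, so some will have AEs still open at the Week 96 visit. Before the first dose of the main study, by contrast, Protocol 5.3.1 has only serious events caused by protocol procedures reported, so few AE records pre-date Day 1. The worsening limb is therefore missing where more existing records could need it.

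If worsening is not counted, the error runs one way: substudy counts can fall but not rise, in favour of the shorter infusion. The substudy and main-study AE rates would also rest on different definitions of an emergent event.

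**Working it through.** The question is one of definition, so the check sets the rules side by side.

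| | Main study (SAP 4.7) | Substudy (SAP Appendix 6; Protocol Appendix 2) |
|---|---|---|
| New event | Counted | Counted |
| Existing event that worsens | Counted | Not mentioned |
| Reference time | First study dose | Week 96 shorter infusion (SAP); treatment (Protocol) |

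**Step 1: does *occurring* already include worsening?** SAP 4.7 puts the two limbs in one sentence, joined by *or*. If an event that occurs on or after treatment already included an existing event that worsens, the second limb would be redundant. On the SAP's own usage, then, the Appendix 6 phrase covers the first limb only.

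**Step 2: does SAP 4.7 carry over?** Section 4 refers substudy analyses to Appendix 6, which does not refer back to 4.7. Even if 4.7 applied, its reference is the first study dose. It would not separate worsening before Week 96 from worsening after the shorter infusion.

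**Step 3: a hypothetical case.** A Grade 1 AE begins at Week 80 and is still present at Week 96. It reaches Grade 3 after the shorter infusion. Under Protocol 5.3.5.4 it remains one record, with Grade 1 as initial and Grade 3 as most extreme severity. The event began before the infusion, so under the Appendix 6 rule it enters neither the all-AE nor the Grade 3 to 5 table. If *occurring* were instead read to admit every AE still ongoing, the tables would also take in events whose highest grade was reached before the infusion. Neither reading gives a well-defined Grade 3 to 5 table.

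**Step 4: which outputs are exposed?** Protocol 5.3.5.1 defines an IRR as a related event during or within 24 hours after an administration. The previous infusion is at Week 72, so the gap is 96 − 72 = 24 weeks. An IRR to the Week 96 infusion is therefore a new event and is counted. This holds for the Grade 3 or 4 IRR outcome and for the other IRR summaries. The exposed outputs are the general AE tables.

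**Step 5: the plan's own figures.** The substudy precision table gives Clopper-Pearson 95% intervals for 1 to 7 patients with Grade 3 or 4 IRRs out of n = 100. The lower limit is the 0.025 quantile of Beta(x, n − x + 1) and the upper limit is the 0.975 quantile of Beta(x + 1, n − x). For x = 1 this gives 0.03% to 5.45%; for x = 7, 2.86% to 13.89%. All seven rows reproduce to two decimals. They concern IRRs, so by Step 4 the point does not change them.

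**Step 6: size for the exposed tables.** This would need the number of patients with an AE ongoing at Week 96 and the share that worsen by the follow-up visit about 30 days later. The documents give neither.

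**The case against.** The strongest reply is that *occurring on or after treatment* is stock protocol wording. Protocol 6.6.2 uses it for the main study, and the SAP turned it into a definition that includes worsening, so the same intent may be presumed for the substudy. Further data-handling rules and the list of substudy outputs are in DAP Module 2, and the eCRF is not part of the documents, so the gap may be closed elsewhere. What stands is that exclusion was perhaps not intended. But the SAP wrote the worsening limb out where it wanted it, and Appendix 6 omits it without referring back.

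There are also partial safeguards. Protocol Appendix 2 asks for worsened clinically significant examination findings after dosing to be recorded as AEs where appropriate. Appendix 6 separately counts patients whose infusion was slowed, interrupted or stopped. These stand, but the first covers examination findings only and does not set aside the single-record rule for an AE already on file. The second covers only events that changed the infusion.

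Four stronger readings are tempting, and the documents do not support them:

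- *The primary result is biased.* It is not, because a Week 96 IRR is always a new event. The IRR precision table therefore cannot illustrate the effect of a missed case.
- *The number missed can be estimated.* The 83.3% of patients with an AE in the pooled relapsing MS trials (Protocol 1.2.1.2) refers to any AE over 96 weeks, not to AEs still open at the end.
- *The events are lost to the study.* An AE that began after Day 1 already meets the first limb of SAP 4.7, that definition has no end date, and the final analysis follows the substudy visits (SAP 2.4). What is missing is attribution to the shorter infusion.
- *The protocol fixes the original onset date.* Protocol 5.3.5.4 does not mention the onset date, and it does date a change to serious. That the event counts as having begun before the infusion is an inference from the single record.

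**Conclusion.** The point holds as a gap in definition, of modest consequence. Followed as written, Appendix 6 leaves an AE that was ongoing at Week 96 and worsened after the shorter infusion out of the substudy's general AE tables: all AEs, Grade 3 to 5, serious and treatment-related. The direction is known: those counts can only be too low. The size is not, and no number should be attached to it.

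The conclusion rests on two assumptions: that *occurring* has the meaning SAP 4.7 gives it, and that no unseen programming specification supplies a worsening rule for the substudy. Even if the second fails, the rule belongs in the SAP, because it decides what the safety tables count.

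**What to change.** In SAP Appendix 6, with a matching line in Protocol Appendix 2, define a substudy treatment-emergent AE as one that starts, or an existing AE that increases in grade or becomes serious, on or after the start of the Week 96 shorter infusion. This is the SAP 4.7 rule with the reference moved to that infusion.

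Keep the single-record rule of Protocol 5.3.5.4. Entering the worsening as a new AE would contradict that rule and count one persistent event twice in event-based summaries, such as the rates per 100 patient-years in SAP 4.7.2. Identify worsening on the existing record instead:

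- for seriousness, from the date the event became serious, which is already required;
- for grade, by comparing the grade of each AE ongoing at the Week 96 visit, before the infusion, with its most extreme grade between then and the substudy follow-up visit, and noting the date of any increase on that record.

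The comparison should use the grade at Week 96, not the initial grade, so that a peak reached before the infusion is not attributed to it.

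The cost is a short definition in each document, slightly more data handling for AEs open at Week 96, and a slightly less favourable AE rate. No visit or procedure is added. For patients already treated in the substudy when the change is made, the Week 96 grade may have to come from the medical record; where it cannot be recovered, the event can be listed.

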### **Exposure of Study Medication**

Ocrelizumab exposure will be summarized including duration of the shorter-infusion drug administration, actual volume and dosage of ocrelizumab administered.

Number and percentage of patients who experienced shorter infusion interventions (slowing, interruption or stopping) will be summarized.

Duration of the shorter infusion will also be summarized for patients who experienced each type of interventions and for patients who did not experience any intervention separately.

### **Laboratory Data**

A summary of the number and percentage of patients with abnormal laboratory outcomes will be produced for each laboratory parameter.

### **Vital Signs**

Changes in physical findings and vital signs with onset on or after the shorter infusion at Week 96 and at the substudy follow-up visit will be summarized.

## **Missing Data**

Missing and partial dates for AEs will be handled according to Roche STREAM algorithm.

For partial or missing shorter infusion administration start/end time, data will not be imputed considering the potential impact of imputed time points on the duration of the shorter infusion (about 2 hours).

Missing assessments for continuous variables, such as physical examinations and vital signs, will not be imputed.

## **Interim Analyses**

No formal interim analysis is planned for the substudy. Interim looks may be performed for safety monitoring or publication purpose.

## **Scope of Planned Analyses**

The final substudy analysis will include all patients and all data collected during the shorter infusion study period (including Week 96 and the safety follow up period).

Specific list of planned outputs will be available in DAP Module 2.

## Appendix A

### Schedule of Assessments

|   | Week 96
Treatment Visit
( $\pm 14$ days) | Substudy
Follow-up Visit
( $30 \pm 14$ days later) a |
|---|--|---|
| Informed consent b                                   | x  |   |
| Review inclusion and exclusion criteria                         | x  |   |
| Physical examination c                               | x  | x   |
| Weight  | x  |   |
| Vital signs d  | x  | x   |
| Brain MRI e  | x  |   |
| Pregnancy test f                                     | x  |   |
| Adverse event assessment g                           | x  | x   |
| Concomitant treatment review                                    | x  | x h  |
| Methylprednisolone and antihistamine premedication i | x  |   |
| Ocrelizumab administration                                      | x  |   |

eCRF=electronic case report form; IRR=infusion-related reaction; IV=intravenous; MRI=magnetic resonance imaging; PML=progressive multifocal leukoencephalopathy.

- a Conducted 30 days after the shorter infusion with ocrelizumab.
- b Written informed consent will be obtained from all patients in order to be eligible for the study and prior to any study procedures.
- c A limited physical examination may be conducted. Any abnormality identified should be recorded on the eCRF. New or worsened clinically significant abnormalities should be recorded as adverse events, if appropriate
- d Vital signs will include the measurements of heart rate, systolic and diastolic blood pressures, and temperature. Vital signs should be taken approximately 45 minutes prior to the premedication methylprednisolone infusion. In addition, vital signs should be obtained prior to the ocrelizumab infusion then approximately every 15 minutes for the first hour, followed by approximately every 30 minutes until 1 hour after the end of the infusion.
- e Should only be done if PML is suspected, and should not be done in addition to an MRI at Week 96 conducted in the main study. If needed, should be done pre-dose.
- f Pregnancy test should not be done in addition to the pregnancy test at Week 96 conducted in the main study. If needed, should be done pre-dose.
- g After informed consent has been obtained but prior to initiation of study drug, only serious adverse events caused by a protocol-mandated intervention (e.g., invasive procedures such as biopsies, discontinuation of medications) should be reported. After initiation of study drug, related serious adverse events must be collected and reported regardless of the time elapsed from the study drug administration, even if the substudy has been closed. Unrelated serious adverse events must be collected and reported during the substudy and substudy follow-up. Non-serious adverse events have to be reported until the end of substudy follow-up.
- h Medications used after treatment discontinuation should be recorded during substudy follow-up.
- i All patients must receive prophylactic treatment with 100 mg methylprednisolone (or equivalent), to be completed approximately 30 minutes before the start of each ocrelizumab infusion, and with an antihistaminic drug (e.g., diphenhydramine) approximately 30–60 minutes before each infusion of ocrelizumab. Prophylactic treatment with an analgesic/antipyretic

(e.g., 1 g acetaminophen) is strongly recommended 30–60 minutes prior to the start of ocrelizumab infusion to reduce the risk of IRRs.

## **Appendix B**

### **Infusion rates for 600-mg ocrelizumab Shorter Dose**

| Time (min) | Infusion rate (mL/hr) | Infusion rate (mg/hr) | Max Dose per Interval (mg) | Cumulative Dose (mg) |
|------------|-----------------------|-----------------------|----------------------------|----------------------|
| 0–15       | 100                   | 120                   | 30                         | 30                   |
| 15–30      | 200                   | 240                   | 60                         | 90                   |
| 30–60      | 250                   | 300                   | 150                        | 240                  |
| 60–90      | 300                   | 360                   | 180                        | 420                  |
| 90–120     | 300                   | 360                   | 180                        | 600                  |

Infusion time: 120 min.

Preparation per U.S. label: 600 mg ocrelizumab/500 mL normal saline toward a drug concentration of approximately 1.2 mg/mL.

